#### Specific Aims:

**Specific Aim 1: Determine whether a 7-week course of daily brivaracetam reduces below-level neuropathic pain in SCI.** The objective of this aim is to assess efficacy of a 7-week course of brivaracetam to reduce neuropathic pain in men and women with SCI. We will assess change in pain intensity and related outcomes, including mood, satisfaction with life, and community integration. We will monitor drug adverse events and tolerability.

**Specific Aim 2: Determine whether a 7-week course of daily brivaracetam increases parietal operculum brain connectivity.** The objective of this exploratory aim is to assess the effect of a 7-week course of brivaracetam treatment on parietal operculum activation and connectivity in SCI. We will assess changes in cortical activity of related pain perception regions and networks in the brain in response to brivaracetam treatment compared to placebo using rsfMRI and pain-related task-based fMRI. To achieve this aim, we will test the working hypothesis that brivaracetam increases parietal operculum activation and connectivity compared to placebo, using rsfMRI, task-based fMRI, and a validated image processing protocol. We will also examine changes in network connectivity and brain activity in the insula, because of its concurrent reported importance for neuropathic pain in SCI. We will assess the association between functional connectivity of the parietal operculum and the insula and change in pain intensity in response to brivaracetam treatment.

**Specific Aim 3: Determine whether baseline microRNA-485 levels are associated with response to brivaracetam treatment.** The objective of this exploratory aim is to assess microRNA expression as a potential predictive biomarker of response to brivaracetam treatment. To achieve this, we will test the working hypothesis that baseline circulating miR-485 levels predict change in pain intensity in response to brivaracetam treatment. To test this, we will use Next-Generation sequencing. We will assess miR-485 levels at baseline and after a three-month treatment course.

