These preliminary findings suggest that SCI disrupts multiple brain networks, along with significant alteration of resting state function of the paracingulate gyrus. Pain may modulate some of these properties, and notably disrupts local brain activity of the periaqueductal gray. The frequency band of ALFF alterations are similar to those of calcium channels and astrocytes, consistent with findings in post-traumatic neuralgia [Alshelh et al., 2016]. Further, the primary somatosensory region representing the lower torso displayed an increase in intrinsic connectivity in parallel with increased pain ratings. This may be consistent with phantom limb like pain, or an increased processing of denervated lower body sensations. Collectively, this work demonstrates feasibility and our expertise with the proposed imaging methodology. ALFF has high test-retest reliability and is thus suitable for longitudinal evaluations [Zuo et al., 2010]. Based on these findings, we hypothesize that brivaracetam treatment will normalize pain-related changes identified above, with ALFF of the periaqueductal gray being the primary outcome. Therefore, these findings provide the scientific rationale for the fMRI studies proposed in Aim 2.

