### **4.0 Study Intervention(s)/Investigational Agent(s)**

Description:

Intervention: brivaracetam or placebo administration. [name] (Co-I/study physician) currently holds an Investigational New Drug (IND) application for brivaracetam to treat severe neuropathic pain in individuals with SCI (IND # 150388). With regulatory support provided by UMN CTSI, we will submit this protocol to the FDA for review under the existing IND upon notification of funding. RxArtisans Pharmacy (Wayzata, MN) will FedEx the drug to the participant directly (study staff will send an email notification to the participant that the drug has been sent by overnight

mail) or to the designated contact at the enrolling site for distribution. To minimize wasting of drug, RxArtisans will dispense and ship prescriptions concurrent with the ramp-up schedule (weekly, biweekly, or as requested by study doctor). Participants will be asked to verify by phone or email receipt of study drug and initiation of the treatment course.

Drug dosage will be individually titrated for each participant with a goal of 100mg BID according to the following dose escalation protocol that we use clinically: 50mg BID for 1 week followed by 100mg BID for 28 days as tolerated. Participants will be allowed to reduce the dose of brivaracetam if they experience unacceptable side effects defined as increased somnolence according to routine clinical practice with other drugs in this class used for pain. Participants will be given an additional week to ramp up to 100mg BID, as needed. The 28-day treatment period might also be extended in the case of illness or other unanticipated event that impacts the ability to take the medication consistently. This will be determined on a case-by-case basis by the study team. The treatment course will be recorded and considered in analysis. A dose of 50mg BID or higher must be maintained to complete the trial. The study drug will be paid for by the study.

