- iii. Task 3: Whole-body movement task. Participants will perform a kinesthetic imagery of a whole-body movement, in which the hands are moving away and closer to the body symmetrically with guided breathing after viewing a video demonstration of the movement. We chose task 3 based on studies that demonstrate substantial spatial overlap of areas activated during motor imagery vs. motor execution. Our prior studies showed OP1/OP4 and posterior parietal cortex activation during this task in adults with chronic low back pain. We showed stronger insula connectivity after CMR in adults with SCI/D.
- iv. Task 4: Sensory stimulation task of the pads of the big toes and thumbs with a towel. Participants will not be made aware of when stroking occurs and will be asked after the scan if they sensed any hand or foot stimulation and, if so, where exactly they felt the stimulation.
- v. Task 5: Finger tapping. The participant is instructed verbally to tap their right fingers

MEDICAL PROTOCOL (HRP-590)

PROTOCOL TITLE: Brivaracetam to Reduce Neuropathic Pain in Chronic SCI: A Randomized, Double-Blind, Placebo-Controlled Clinical Trial

VERSION DATE: v7.0 APR2024

- vi. Task 6: Toe tapping. The participant is instructed verbally to tap their right foot. The task is alternated with rest.

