#### Aim 2 statistical analysis

fMRI data will be processed using the conn functional connectivity toolbox with established standardized controls for multiple comparisons (SPM family wise error correction methods). Data will undergo realignment, scrubbing, artifact detection, and CompCor denoising. Primary analyses will focus on OP1/OP4 and insula regions-of-interest for resting-state connectivity and exploratory multivariate pattern analyses. Task-based fMRI will undergo the same preprocessing pipeline and will be modeled with a general linear model. Within-group pre-post changes in task-based brain activation and resting-state connectivity will be tested using paired t-tests or Wilcoxon signed-rank tests.

Between-group differences of pre-post changes in these measures will be tested using 2 sample t-tests or Mann-Whitney U tests. Mixed effects models with correlated errors will also be used to test the effect of CMR on brain imaging outcomes after adjusting for potential confounders, which will include the subject-level effect, time, group indicator, and time-by-group interaction as predictors, and age, race, and other covariates as appropriate. We will use False Discovery Rate (FDR) correction to control for the overall Type 1 errors for the voxel-level analyses. We will test the correlation between changes in brain function and clinical measures of sensory and

motor function using Pearson's correlations coefficients with 95% confidence interval calculated based on Fisher's Z transform.

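### The Aim 2 analysis text in Section 15.3 does not match Aim 2: it names CMR as the treatment, specifies no imaging–pain association, and conflicts with Section 2.2 on the primary imaging outcome

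*Combined protocol and SAP*

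**What the plan says.** Section 4.0 defines the treatment: "Intervention: brivaracetam or placebo administration". Specific Aim 2, labelled exploratory, states the association to be studied: "We will assess the association between functional connectivity of the parietal operculum and the insula and change in pain intensity" in response to brivaracetam.

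The Aim 2 paragraphs of Section 15.3 say the following.

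- On regions: "Primary analyses will focus on OP1/OP4 and insula regions-of-interest for resting-state connectivity", together with exploratory pattern analyses.
- On the treatment effect: two-sample tests of between-group differences in pre-post change, and then "Mixed effects models with correlated errors will also be used to test the effect of CMR on brain imaging outcomes". The predictors listed for that model include a group indicator and a time-by-group interaction.
- On the imaging–clinical link: "We will test the correlation between changes in brain function and clinical measures of sensory and" motor function, by Pearson correlation with a Fisher Z confidence interval.

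Section 2.2 closes its imaging preliminary data with the hypothesis that brivaracetam will normalise the pain-related changes found there, "with ALFF of the periaqueductal gray being the primary outcome". It gives those findings as the rationale for the Aim 2 fMRI work.

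**The concern.** The Aim 2 paragraphs read as though they were partly carried over from another study, and three things follow.

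First, the treatment named in the model is not the trial's treatment. Second, the clinical variable named in the correlation is not one the trial lists, while the variable Aim 2 does name, change in pain intensity, has no analysis attached. Third, two sections of one document give different answers on which imaging outcome is primary.

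The second matters most. Section 2.2 presents parieto-insular function as a candidate predictive biomarker that would inform larger trials, and that needs a link to pain. If the link is first specified after unblinding, the choice of pain variable, time point, region and handling of arm will be post hoc. The third leaves room to choose whichever imaging outcome looks better.

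**Working it through.** There is no stated figure to reproduce; the check is a comparison of sections.

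**Treatment.** Sections 4.0 and 5.0 randomise 1:1 to brivaracetam or placebo. CMR is not an arm and is not in the abbreviation list (CMRR, the imaging centre, is). Its only other use is in the description of fMRI Task 3 in Section 5.0, about earlier work: "We showed stronger insula connectivity after CMR in adults with SCI/D". The documents never expand the term. That it is some other intervention is an inference from that sentence and from its absence among the arms. Since the only groups in this trial are brivaracetam and placebo, the time-by-group term, if fitted as listed, estimates the arm difference in pre-post change.

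**Clinical variable in the correlation.** The places where a sensory or motor function measure could appear are:

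- Section 3.0 outcomes: pain, brain activity and connectivity, psychosocial factors, spasm frequency. None.
- Section 5.0 outcome list: adds opioid use, neuropathic pain and intervention expectations. None.
- Section 5.0 measures: pain, mood, life satisfaction, participation, trauma, sleep, kinesiophobia, self-efficacy, catastrophizing, disability, spasm, bladder and bowel, expectations, diary, MRI. No sensory or motor examination score.
- Table 1: a physical health exam, with no scored sensory or motor component.

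The nearest items do not fit. The Penn scale is self-reported spasticity. The focused physical exam has no named score. The Task 4 report of toe or thumb stimulation is a post-scan question, not a listed clinical outcome.

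**Analysis for the pain association.** Section 15.1 refers Aim 2 to the approach of the team's other imaging studies and then describes preprocessing. Section 15.2 says the sample size suffices for the exploratory aims. Section 15.3 gives the sensory/motor correlation. None states a model, pain variable, time point or treatment of arm for connectivity against change in pain.

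**Primary imaging outcome.** Section 2.2: ALFF, periaqueductal gray. Section 15.3: resting-state connectivity, OP1/OP4 and insula, with no mention of ALFF or the periaqueductal gray. The hypothesis in Section 1.1 names OP1/OP4 connectivity alone. Specific Aim 2 names parietal operculum activation and connectivity, by resting-state and task fMRI.

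**Illustrative size of the multiplicity.** Three candidate regions (periaqueductal gray, OP1/OP4, insula), each tested at 5%, assumed independent and uncorrected across regions:

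1 − 0.95³ = 1 − 0.857 = 0.143, about 14%.

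Positive correlation between the tests would lower this.

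**What the missing correlation could detect.** With the plan's own Pearson/Fisher Z method, 80% power and two-sided 5%, the detectable correlation is r = tanh((1.960 + 0.842)/√(n − 3)). The number scanned is not stated: MRI is optional, and remote participants and those with MRI contraindications have none. The n below are therefore assumptions, up to the 40 completers expected in Section 10.0.

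| n scanned | detectable r |
|---|---|
| 40 | 0.43 |
| 30 | 0.49 |
| 20 | 0.59 |
| 10 | 0.79 |

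This is context for how simple the analysis should be, not evidence of the mismatch.

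**The case against.** The strongest reply is that little here changes what would be estimated. The mixed model contains the group and time-by-group terms, and the two-sample tests compare the same arms, so CMR is a slip in one sentence. That stands: a reader might infer that the imaging analysis would test a different intervention or could not be run, and the listed predictors do not support that.

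A reader might also infer that the connectivity–pain association will never be analysed. The documents support only that no analysis is specified. Aim 2 states the intent, pain intensity is the primary endpoint and will be collected, and Section 15.3 supplies a usable correlation method attached to the wrong clinical variable. One could try to read sensory function as pain, since Section 5.0 calls pain intensity the sensory dimension of the Brief Pain Inventory. Next to motor function that reading is strained, and it still would not identify the pain variable.

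On multiplicity, a reader might cross three regions with rest and six tasks, giving 3 × 7 = 21 tests and 1 − 0.95²¹ = 66%. The documents do not support that family. Section 15.3 confines its primary focus to resting-state connectivity, the preliminary-data section presents ALFF as a resting-state measure, and no task analysis of the periaqueductal gray is planned. Section 15.3 also plans SPM family-wise correction and voxel-level FDR. It does not state that either covers the choice among regions or between the two statements of what is primary, so the 14% remains an illustration.

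Finally, Aim 2 is exploratory, imaging is a secondary outcome, and the trial calls itself a pilot. That limits the severity. It does not excuse a stated objective with no analysis, or a planned correlation with unlisted measures.

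**Conclusion.** Section 15.3 and Aim 2 disagree on three points: a wrong treatment name that does not alter the contrast, an imaging–clinical correlation aimed at measures the trial does not list while the promised pain association has no specified analysis, and a primary imaging focus that differs from Section 2.2. The second is the substantive gap. The third leaves the primary imaging outcome open to later choice.

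The conclusion rests on the text and on no assumed effect size or variance. It does assume that the unscored physical exam is not meant as the sensory and motor measure; if it is, the plan must say so, and the pain association would still be missing. The primary pain endpoint, its test and its sample size are untouched. This should be corrected, but it is not critical to the trial's main result.

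**What to change.** 1. In the mixed-model sentence, replace CMR with brivaracetam versus placebo, and identify the time-by-group term as the treatment effect.
2. Replace the sensory/motor correlation with the association between change in connectivity (OP1/OP4 and insula) and change in International SCI Pain Data Set pain intensity, from baseline to Visit 3. Account for arm, because a correlation pooled over arms can arise merely from the drug moving both quantities. An arm-adjusted analysis, one region at a time, is a reasonable choice given the unknown number scanned. Either name the sensory and motor measures and where they are collected, or drop them.
3. Reconcile Sections 2.2 and 15.3 before unblinding. Designate one primary imaging outcome, or one OP1/OP4 and insula family with a stated correction across it. Label periaqueductal gray ALFF and the task analyses secondary or exploratory. Which outcome to choose is the investigators' decision, because the documents do not settle on one.

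The cost is a rewritten paragraph in Section 15.3 and an edited sentence in Section 2.2. The pain scores and optional scans needed are already planned, so no visit or procedure is added.

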#### *15.4* Data Integrity:

Study staff will collect and store data. Data will be collected electronically or on paper forms. All electronic data will be stored on Box Secure Storage or REDCap. Paper forms will only be accessible by the study staff, trained study coordinator, and the principal investigator. All paper documents will be kept in locked file cabinets in locked offices at all times. Participant names, contact information, health history, and other information that can be traced back to the participant will be kept separately from data collected for the study. Personal information will be kept in a locked office and away from data or in a separate folder on Box Secure Storage. Protocol sheets used during data collection will only have the participant's ID.

Data integrity of the data acquisition will be tested at the time of acquisition. Both the MRI technician and the PI or study staff will be present to monitor the data in real life.

All study records will be kept indefinitely after the study is closed. Research records will be stored in a manner to protect the confidentiality of participant information.

Drs. [name] and [name] will review data monthly. They will be responsible for monitoring the completeness of all data and source documents as well as monitoring the informed consent procedures. Checklists and note pages are used to note any deviations or omissions from the protocols. Any deviation to the protocol that may have an effect on the safety or rights of the volunteer, or the integrity of the study will be promptly reported to the IRB.

## **16.0 Health Information and Privacy Compliance**

### *16.1* Select which of the following is applicable to your research:

- ☐ My research does not require access to individual health information.
- ☒ I am requesting that all research participants sign a HIPCO approved HIPAA Disclosure Authorization to participate in the research (either the standalone form or the combined consent and HIPAA Authorization).
- ☐ I am requesting the IRB to approve a Waiver or an alteration of research participant authorization to participate in the research.

MEDICAL PROTOCOL (HRP-590)

PROTOCOL TITLE: Brivaracetam to Reduce Neuropathic Pain in Chronic SCI: A Randomized, Double-Blind, Placebo-Controlled Clinical Trial  
VERSION DATE: v7.0 APR2024

Appropriate Use for Research:

Identify the source of Private Health Information you will be using for your research (Check all that apply)

☐ I will use the Informatics Consulting Services (ICS) available through CTSI (also referred to as the University's Information Exchange (IE) or data shelter) to pull records for me

☒ I will collect information directly from research participants.

☐ I will use University services to access and retrieve records from the Bone Marrow Transplant (BMPT) database, also known as the HSCT (Hematopoietic Stem Cell Transplant) database.

☒ I will pull records directly from EPIC.

☐ I will retrieve record directly from axiUm / MiPACS

☐ I will receive data from the Center for Medicare/Medicaid Services

☐ I will receive a limited data set from another institution

☒ Other. Describe:

A screening phone survey to determine eligibility will be completed and stored in paper format and/or in REDCap. After consent, a health survey will be collected in paper format and stored in the participants study file.

16.2 Explain how you will ensure that only records of patients who have agreed to have their information used for research will be reviewed.

The team will access PHI for screening purposes according to institutional policies. The team will access and record PHI for data collection only after receiving permission from each enrolled study participant.

16.3 Approximate number of records required for review: 60

16.4 Please describe how you will communicate with research participants during the course of this research. Check all applicable boxes

☐ This research involves record review only. There will be no communication with research participants.

Indicate if data will be collected, downloaded, accessed, shared, or stored using a server, desktop, laptop, external drive or mobile device (including a tablet computer such as an iPad or a smartform (iPhone or Android devices) that you have not already identified in the preceding questions

☐ I will use a server not previously listed to collect/download research data

☐ I will use a desktop or laptop not previously listed

☐ I will use an external hard drive or USB drive ("flash" or "thumb" drives) not previously listed

☐ I will use a mobile device such as a tablet or smartphone not previously listed

16.6 Consultants. Vendors. Third Parties: -

*LC Sciences*

We will send blood serum samples to LC Sciences (Houston, TX) to perform microRNA analysis (non-genomic analysis). LC Sciences will have access to de-identified data only.

*REDCap eConsent*

The informed consent form and HIPAA form will be signed with an eSignature using REDCap. The REDCap eConsent process is a 21 CFR Part 11 compliant method for electronic signature capture. For more information on REDCap compliance, please visit:

[https://redcap.ahc.umn.edu/surveys/?s=3PT9FY73NC&topics\\_\\_\\_ec=1#ec](https://redcap.ahc.umn.edu/surveys/?s=3PT9FY73NC&topics___ec=1#ec)

Links to identifiable data:

The research data will be collected on RedCap and on the MRI. Those data will not contain personal identifiable information. Only the PIs and designated study staff will have a document that links the name with the code, which will be kept secure on the University Box secure storage.

Sharing of Data with Research Team Members:

Only deidentified data will be shared with team members. The PIs and clinical trial coordinators will have access to identifiable information for contact purposes.

Storage and Disposal of Paper Documents:

Documents will be stored in a secure closet behind secure doors in the PI and Co-PI's offices and labs. Documents that need to be disposed will be disposed of in secure bins and then shredded.

## **17.0 Confidentiality**

Data Security:

Clinical data will be stored on Research Electronic Data Capture (REDCap) and on HIPAA protected encrypted servers. Participant confidentiality will be safeguarded by password protected databases and locked file cabinets. Research records will be stripped of identifying information, with keys identifying participants available only to the PI or selected study-related personnel who have met the necessary Responsible Conduct of Research, HIPAA, human participants, data security and study specific training requirements. Brain imaging will be acquired via standardized protocols. Brain imaging will be acquired via standardized protocols. MRI data acquisition will not contain personal health information. The MRI data will be stored in digital form on encrypted servers.

Information about study participants will be kept confidential and managed according to the requirements of the Health Insurance Portability and Accountability Act of 1996 (HIPAA). Those regulations require a signed participant authorization informing the participant of the following:

- What protected health information (PHI) will be collected from participants in this study
- Who will have access to that information and why
- Who will use or disclose that information
- The rights of a research participant to revoke their authorization for use of their PHI.

In the event that a participant revokes authorization to collect or use PHI, the investigator, by regulation, retains the ability to use all information collected prior to the revocation of participant authorization. For participants that have revoked authorization to collect or use PHI, attempts should be made to obtain permission to collect at least vital status (i.e., that the participant is alive) at the end of their scheduled study period.

Procedures are in place for maintaining the full confidentiality of all information collected. Participant confidentiality will be protected by securing all hard copy study files in locked filing cabinets. Electronic files containing personal identifiers will be stored on Box Secure Storage or REDCap. All study staff receive training on privacy standards for maintaining participant confidentiality. All published reports will be of summary nature and no individual participants will be identified beyond the investigative staff involved in the project.

REDCap includes a complete suite of features to support HIPAA compliance, including a full audit trail, user-based privileges, and integration with the institutional LDAP server. The MySQL database and the web server will both be housed on secure servers operated by the UMN Academic Health Center's Information Systems group (AHC-IS). The servers are in a physically secure location on campus and are backed up nightly, with the backups stored in accordance with the AHC-IS retention schedule of daily, weekly, and monthly tapes retained for 1 month, 3 months, and 6 months, respectively. Weekly backup tapes are stored offsite. The AHC-IS servers provide a stable, secure, well-maintained, and high-capacity data storage environment, and both REDCap and MySQL are widely-used, powerful, reliable, well-supported systems. Access to the study's data in REDCap will be restricted to the members of the study team by username and password.

The informed consent form and HIPAA form will be signed with an eSignature using REDCap. The REDCap eConsent process is a 21 CFR Part 11 compliant method for electronic signature capture. For more information on REDCap compliance, please visit:

[https://redcap.ahc.umn.edu/surveys/?s=3PT9FY73NC&topics\\_\\_\\_ec=1#ec](https://redcap.ahc.umn.edu/surveys/?s=3PT9FY73NC&topics___ec=1#ec)

Data files will be stored locally at the UMN Department of Rehabilitation Medicine. All data are stored on a secure HIPAA protected PC, and on secure HIPAA protected servers (Box Secure Storage). Raw and processed brain imaging data are also stored by the biostatistician/brain imaging

analysis specialists responsible for brain analysis and are backed up weekly.

Training: All study staff will be appropriately trained in data security.

Authorization of access: Only designated IRB-approved staff will have access to the data.

Password protection/encryption/physical controls: All data will be stored in REDCap/Box.

Separation of Identifiers: Study staff will keep the mapping of identification code to the identity of the participant in a database protected by two-levels of password protection stored separately from the data on Box.

